### **Pre- and Post- Surgery Tests**

The PROM scores at each post-surgery visit will be compared with the baseline score via a t-test for two related samples or via the nonparametric Wilcoxon Rank Sum test for nonnormally distributed scores.

### **Group Comparisons**

At each post-surgery visit, the patient reported outcome (PROMIS, AOS and FAOS) score and the change from baseline scores will be analyzed. Analysis of covariance (ANCOVA) with baseline score as a covariate factor will be implemented for all comparisons (i.e., comparison by disease diagnosis). The components of the ANCOVA model are: baseline scores, subgroups or independent factor and subgroup-by-baseline interaction.

Adjusted mean of subgroups with 95% confidence intervals will be presented. Bonferroni pairwise adjusted comparison of means will be done when significant differences among the group is established.

All statistical analysis tables for PROMIS, AOS and FAOS will be will have the elements as presented in the template below.

Visit	Factor (or sub-factor X)	All Subjects (N=xx)	Group 1 (N=xx)	Group 2 (N=xx)
Pre-operative	N	XX	XX	XX
-	Mean $\pm$ SD	$xx.x \pm xx.x$	$xx.x \pm xx.x$	$xx.x \pm xx.x$
	1st Q, Median, 3rd Q	XX.X, XX.X, XX.X	XX.X, XX.X, XX.X	XX.X, XX.X, XX.X
	Min, Max	XX.X , XX.X	XX.X , XX.X	XX.X , XX.X
	Difference in means			XX.X
	p-value for mean difference*=0			X.XXX
Post-op Visit	Ν	XX	XX	XX
-	Mean $\pm$ SD	$xx.x \pm xx.x$	$xx.x \pm xx.x$	$xx.x \pm xx.x$
	1st Q, Median, 3rd Q	xx.x, xx.x, xx.x	XX.X, XX.X, XX.X	xx.x, xx.x, xx.x
	Min, Max	XX.X , XX.X	XX.X , XX.X	XX.X, XX.X
	p-value for change from baseline***	X.XXX	X.XXX	X.XXX
	Difference in group means			XX.X
	p-value for group difference**=0			X.XXX
	Adjusted mean $\pm$ se**		$xx.x \pm xx.x$	$xx.x \pm xx.x$
	95% CI for the Difference in Mean**			(xx.x , xx.x)
	Change from Baseline			
	N	XX	XX	XX
	Mean $\pm$ SD	$xx.x \pm xx.x$	$xx.x \pm xx.x$	$xx.x \pm xx.x$
	1st Q, Median, 3rd Q	xx.x, xx.x, xx.x	xx.x, xx.x, xx.x	xx.x, xx.x, xx.x
	Min, Max	XX.X , XX.X	XX.X , XX.X	XX.X, XX.X
	Difference in group means			XX.X
	Adjusted mean ± se**		$xx.x \pm xx.x$	$xx.x \pm xx.x$
	95% CI for the Difference in Mean**			(xx.x , xx.x)
	p-value for group mean difference=0**			X.XXX

Table 3	. Template	of statistical	tables for	PROMIS,	AOS and FAOS
---------	------------	----------------	------------	---------	--------------

Note: Results will be presented for each post-operative visit.

\*One-way analysis of variance for group difference. \*\*Results of ANCOVA, group variable as fixed effect and baseline as covariate, means adjusted for baseline.

\*\*\*t-test or Wilcoxon test p-value for two related samples.

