### Test of assumptions

The normality assumption of ANCOVA will be assessed through the Shapiro-Wilk test. Another important assumption of ANCOVA is that the relationship between the dependent factor and the covariate for each subgroup are the same. The regression slope of response factor on the covariate at each subgroup will be tested for equality. The Levene's test will be implemented to test the assumption of homogeneity of regression slope of response factor on the covariate at each subgroup.

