## Foot and Ankle Outcome Score (FAOS)

FAOS is a self-report measure that evaluates symptoms and functional limitations in individuals with generalized foot and ankle disorders. Items for the FAOS were adapted from the Knee Injury and Osteoarthritis Outcome Score. The FAOS is composed of the

Page 14 of 23

following 5 subscales: pain (9 items), other symptoms (7 items), activities of daily living (7 items), sports and recreational activities (5 items), and foot and ankle-related quality of life (4 items). Each of the FAOS subscale are standardized so that score ranges from 0 to 100, where 100 indicates no problems and 0 indicates extreme problems.

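### The post-operative PROM subgroup ANCOVA makes no allowance for unequal variances, and the plan's only variance test is assigned to slopes with no action attached

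*SAP*

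**What the plan says.** SAP, Group Comparisons: "Analysis of covariance (ANCOVA) with baseline score as a covariate factor will be implemented for all comparisons". The model is specified as follows: "The components of the ANCOVA model are: baseline scores, subgroups or independent factor and subgroup-by-baseline interaction". On output: "Adjusted mean of subgroups with 95% confidence intervals will be presented". On follow-up tests: "Bonferroni pairwise adjusted comparison of means will be done when significant differences among the group is established". The ** footnote of Table 3 describes the ANCOVA with group and baseline only. Neither place mentions group-specific variances or robust standard errors.

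SAP, Test of assumptions, covers two assumptions: normality ("The normality assumption of ANCOVA will be assessed through the Shapiro-Wilk test") and equal slopes. On slopes it adds: "The Levene's test will be implemented to test the assumption of homogeneity of regression slope of response factor on the covariate at each subgroup". Equal residual variance is not named as an assumption, and nothing is said about what happens if a check fails. By contrast, the section on pre- and post-surgery tests gives the paired comparisons a nonparametric alternative.

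The factors in General Considerations include diagnosis (three groups), COFAS type (four groups), and linear and cystic radiolucency (present or absent). The table list adds rheumatoid arthritis against the other two diagnoses combined, and study site.

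**The concern.** A pooled residual variance is a weighted average dominated by the larger groups. If a small group is more variable than a large one, the pooled figure understates the uncertainty of that small group's mean, so differences are declared too often and the 95% interval covers too little. If the small group is less variable, the interval is too wide and power is lost.

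The planned factors could easily produce uneven groups, and missing data are not imputed, so groups can shrink further at late visits. Unequal spread is also plausible on bounded scales: "Each of the FAOS subscale are standardized so that score ranges from 0 to 100", and the AOS has the same range, so a group close to the good end of the scale may show less spread. That is a reason to allow for unequal variance, not evidence that it is present.

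At stake are the adjusted-mean standard errors, intervals and p-values in the post-operative rows of Table 3, repeated over several factors, scores and visits.

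**Working it through.** **Inputs from the documents.** At most 155 patients (SAP, Study Design, Overview); ANCOVA with baseline; 95% intervals. There is no plan figure to reproduce: the protocol says the sample size was not derived statistically, and no subgroup size, SD or power is given.

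**Assumptions.** Two-sided 5% level (not stated in the SAP); a common residual variance, as in standard ANCOVA; splits of 155 and SD ratios r (smaller group's residual SD divided by the larger's) as shown below.

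**Closed form, two groups.** With sizes n1 and n2, N = n1 + n2, and SDs r and 1:

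k = pooled SE / true SE = sqrt{ [(n1·r² + n2)/N]·(1/n1 + 1/n2) / (r²/n1 + 1/n2) }

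Actual type I error = 2·[1 − Φ(1.96·k)].

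Example, 15 v 140, r = 1.5: pooled variance = (15 × 2.25 + 140)/155 = 1.121. Multiplying by (1/15 + 1/140) = 0.0738 gives 0.0827. The true variance is 2.25/15 + 1/140 = 0.1571. So k = sqrt(0.0827/0.1571) = 0.726, and the error is 2·[1 − Φ(1.422)] = 15.5%.

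**Simulation.** 8,000 runs per cell, baseline plus group. The Monte Carlo standard error at 5% is sqrt(0.05 × 0.95/8000) = 0.24 points. The HC3 column uses residual degrees of freedom.

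| Split | r | k | Closed form | Pooled ANCOVA | HC3 | Group variances, Satterthwaite df |
|---|---|---|---|---|---|---|
| 15 v 140 | 0.67 | 1.373 | 0.7% | 0.8% | 5.0% | 4.8% |
| 15 v 140 | 1.0 | 1.000 | 5.0% | 5.0% | 5.7% | 5.2% |
| 15 v 140 | 1.5 | 0.726 | 15.5% | 15.8% | 5.8% | 5.2% |
| 15 v 140 | 2.0 | 0.590 | 24.8% | 24.4% | 5.8% | 5.1% |
| 31 v 124 | 0.67 | 1.262 | 1.3% | 1.3% | 4.6% | 4.8% |
| 31 v 124 | 1.5 | 0.791 | 12.1% | 11.2% | 4.7% | 4.6% |
| 47 v 108 | 1.5 | 0.859 | 9.2% | 9.7% | 5.5% | 5.5% |
| 77 v 78 | 1.5 | 0.998 | 5.1% | 4.9% | 4.7% | 4.9% |
| 77 v 78 | 2.0 | 0.996 | 5.1% | 5.3% | 5.0% | 5.3% |

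Adding the subgroup-by-baseline interaction changes little: 24.9%, 15.3% and 0.7% at 15 v 140 for r = 2, 1.5 and 0.67, and 11.4% at 31 v 124 for r = 1.5. HC3 with Satterthwaite-type degrees of freedom stayed at about 4 to 5%.

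**More than two groups.** A pairwise contrast uses the variance pooled over all groups. Take four equal groups with SDs 1, 1, 1.5 and 1.5. The pooled variance is (1 + 1 + 2.25 + 2.25)/4 = 1.625.

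- Two more variable groups: k = sqrt(1.625/2.25) = 0.850, error 2·[1 − Φ(1.666)] = 9.6%.
- Two less variable groups: k = sqrt(1.625/1) = 1.275, error 2·[1 − Φ(2.499)] = 1.2%.
- One of each: k = sqrt(2 × 1.625/3.25) = 1, error 5%.

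Simulation with groups of 39, 39, 39 and 38 and the interaction model gave 9.8% and 1.2% for the first two. HC3 with conservative degrees of freedom gave 3.9% to 4.5%. These are unadjusted pairwise tests.

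**Would Levene's test, redirected to variances, be enough?** Applied to the ANCOVA residuals, it detected r = 1.5 in 47% of runs at 15 v 140 and 72% at 31 v 124, and r = 2 in 89% at 15 v 140. As a gate it is weakest where the distortion is greatest, in small subgroups.

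**The case against.** The strongest reply is that the plan already contains a variance test. Levene's test is one, so a reader who concluded that nothing in the SAP bears on unequal variance would be overlooking it. That part of the reply stands. But the SAP gives the test the job of checking slopes and attaches no consequence to it, so as written it does not protect these comparisons.

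A second reply is scope, and it also stands. A reader might infer that every subgroup display is affected. The pre-operative comparison is a "One-way analysis of variance for group difference", within-group changes use paired tests, and the satisfaction, radiographic and safety subgroups are only summarised. The point is confined to the post-operative ANCOVA rows.

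Third, a reader might infer that the adjusted means are wrong. They are not: pooling changes the standard errors, intervals and p-values, and HC3 leaves the point estimates as they are.

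Fourth, the size rests on assumed splits and SD ratios, and 15 v 140 is a severe split. This is correct. The bounded-scale argument is also limited: the SAP gives a 0 to 100 range for FAOS and AOS but not for PROMIS, and on the AOS the good end is the floor.

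Finally, Table 3 prints each group's N and SD, so a careful reader could notice a problem. Noticing it would not correct the printed interval or p-value.

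**Conclusion.** The point holds as a low-cost improvement to secondary analyses. The common variance is inferred from an unqualified ANCOVA; the SAP does not state it. If subgroup sizes and residual SDs both differ, the nominal 5% test runs at about 15% (15 v 140, SD ratio 1.5), with interval coverage of about 84%, or at below 1% (SD ratio 0.67). The optimistic error falls to roughly 9 to 10% at 47 v 108 with ratio 1.5, and disappears for two equal groups or equal variances. For factors with three or more groups, equal sizes do not fully protect the pairwise contrasts: about 9 to 10% and about 1% in the four-group example.

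A reader might go further and conclude that this trial's subgroup p-values will in fact be inflated. The documents do not support that: no subgroup size or SD is given, and the error can run in either direction. The primary Kaplan-Meier survivorship endpoint is not touched.

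**What to change.** In Group Comparisons and the ** footnote of Table 3, name one method for all post-operative ANCOVA comparisons, including the Bonferroni pairwise contrasts. Suggested text: *Standard errors, confidence intervals and p-values will use the HC3 heteroscedasticity-consistent variance estimator with Satterthwaite-type degrees of freedom, whatever the result of any test of variances.* The degrees of freedom should be stated, because HC3 with residual degrees of freedom ran slightly high (5.7 to 5.8%) in some 15 v 140 cases.

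In Test of assumptions, test equality of slopes with the subgroup-by-baseline interaction. Keep Levene's test only as a descriptive check of residual variances, not as a gate for choosing the method. The Shapiro-Wilk test need not change on this account.

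The cost is a few sentences in the SAP and a change of variance option in the programs, with no new data. The downside is slightly wider intervals when the variances are in fact equal.

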# **PROTOCOL SYNOPSIS**

Study Title	The INFINITY TM Total Ankle Replacement Follow-up (ITAR)
Study Design	Prospective, multi-site, multi-year post-market clinical follow-up study
Study Group	Primary/Unilateral and/or bilateral Total Ankle Arthroplasty subjects implanted with INFINITY TM Total Ankle System
N Subjects	155 patients in 9 sites
Follow-Up Schedule	Subject enrollment will consist of a Pre-operative, Operative, 6 months, 1 yr., 2 yr., 5yr., 7 yr., 10 yr., and an unscheduled visit as needed.
Primary Objective	Evaluate the long-term survivorship of the INFINITY TM implant over 10 years
Secondary Objective(s)	
 
Secondary objectives assessed will be to:
 
Identify and assess the implant for component loosening and/or subsidence, any osteolysis and/or cyst formation through radiographic evaluation early and throughout the lifetime of the implant.
 
Compare the improvements in self-reported physical, mental, and social health measures from pre-op through 10 years post operatively; assessed by PROMIS® Global Health.
 
Compare pain and functional improvement in the Ankle Osteoarthritis Score (AOS), which is a visual analogue scale specifically designed as a modification of the Foot Function Index.
 
Compare the improvement in patient/physician reported function scores from pre-op through 10 years post-operatively, assessed by the FAOS questionnaire.
 
Compare satisfaction of total ankle replacement post operatively utilizing a four-point scale
 
Identify and report the safety of the implant in terms of complications and adverse events.
 

Inclusion Criteria	
 
Subjects to be included in the study must meet all of the following criteria:
 
Be 21 years of age or older at the time of surgery;
 
Diagnosed with unilateral and/or bilateral ankle joint disease;
 
Diagnosed with ankle joint damage from rheumatoid arthritis, post-traumatic, or degenerative arthritis;
 
Willing and able to consent to participate (written, informed consent;
 
Willing and able to attend the requested follow-up visits;
 
A clinical decision has been made to use INFINITYTM Total Ankle
 

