### Ankle Osteoarthritis Score (AOS)

The AOS consist of 2 components: Pain and Disability, with 9 questions each, are used to calculate the Total AOS score. The score is from zero to one hundred with a lower score indicating more normal function

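### The SAP describes the subgroup ANCOVA both with and without a subgroup-by-baseline interaction; fitted literally on raw scores, the first version can test group differences at a pre-operative score of 0

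*SAP*

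**What the plan says.** The SAP describes the subgroup ANCOVA in three places that do not agree.

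- Group Comparisons, body text: "The components of the ANCOVA model are: baseline scores, subgroups or independent factor and subgroup-by-baseline interaction". Nothing is said about centring, or about the baseline value at which groups are compared.
- Group Comparisons, Table 3 footnote, which governs the group p-values, adjusted means and confidence intervals: "Results of ANCOVA, group variable as fixed effect and baseline as covariate, means adjusted for baseline". No interaction is named.
- Test of assumptions: "The regression slope of response factor on the covariate at each subgroup will be tested for equality". Equal slopes are an assumption here. Levene's test is assigned to the check, and no consequence is attached to its result.

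The follow-up step is conditional: "Bonferroni pairwise adjusted comparison of means will be done when significant differences among the group is established". The test that establishes this is not named. No significance level is given; the nearest statement is "Adjusted mean of subgroups with 95% confidence intervals will be presented". The Computing Environment section names SAS 9.4 or higher, but no procedure or type of test.

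The meaning of a zero score is clear for two instruments. For the AOS: "The score is from zero to one hundred with a lower score indicating more normal function". For the FAOS: "100 indicates no problems and 0 indicates extreme problems". The SAP synopsis gives the sample as "155 patients in 9 sites".

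**The concern.** When a model contains group, baseline and their product, the group coefficient is the difference between the fitted lines where baseline equals 0. A programmer who enters the listed terms with scores as recorded, and reads off the Type III group test, tests that difference. A pre-operative AOS of 0 is a perfect ankle, and a FAOS subscale of 0 is the floor of the scale. Neither describes a typical candidate for ankle replacement.

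Two errors could follow. A real subgroup difference at ordinary pre-operative scores could be missed because the fitted lines are extrapolated to 0. Or a modest difference in slopes could be reported as a group difference that is absent at ordinary scores. The same Table 3 block could then show a p-value at 0 beside adjusted means and an interval at the mean baseline.

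The template serves 24 listed tables (3 instruments × 8 factors), each at up to six post-operative visits. The gate matters only for factors with three or more levels, such as diagnosis (three), COFAS type (four) and study site.

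**Working it through.** The plan states no power, effect size or SD for these comparisons, so there is no figure to reproduce. The check asks what the choice of reference baseline would cost.

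**Inputs.** From the SAP: N = 155 (before attrition), the model terms, and the direction of the AOS and FAOS scales. Assumed: two-sided alpha 0.05 (suggested by the 95% intervals), all baseline means and SDs, residual SD 20, within-group slope 0.5.

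**Standard error.** With groups 0 and 1, within-group baseline SD s and a common baseline mean m, the variance of the fitted group difference at baseline x is approximately

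σ² (1/n₀ + 1/n₁) [1 + (x − m)²/s²].

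At x = m the bracket is 1. At x = 0 it is 1 + (m/s)². The ratio of standard errors is therefore k = √(1 + (m/s)²). It does not depend on N. It is the same for the change-from-baseline rows, because subtracting baseline moves every slope by 1 and leaves the group term alone.

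**Power, equal slopes.** For a difference with 80% power at the mean, the standardised effect is 1.960 + 0.842 = 2.802. At baseline 0,

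power = 1 − Φ(1.960 − 2.802/k) + Φ(−1.960 − 2.802/k).

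Example, m/s = 2: k = √5 = 2.24; 2.802/2.24 = 1.25; power = 1 − Φ(0.71) + Φ(−3.21) = 24%.

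| m/s | k | Power at 0 |
|---|---|---|
| 0.5 | 1.12 | 71% |
| 1 | 1.41 | 51% |
| 1.25 | 1.60 | 42% |
| 1.5 | 1.80 | 34% |
| 2 | 2.24 | 24% |
| 3 | 3.16 | 14% |
| 4 | 4.12 | 10% |
| 5 | 5.10 | 8.5% |

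Half the power is gone at m/s of about 1.3.

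**Simulation.** N = 155, two groups, 3,000 runs per case, scores truncated to 0–100. The true difference was set for 80% power at the mean: 2.802 × 20 × √(1/77.5 + 1/77.5) = 9.0 points for a 50:50 split, and 10.39 points for 25:75.

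| Baseline mean (SD) | Test at 0, 50:50 | Test at 0, 25:75 |
|---|---|---|
| 55 (20) | 15.5% | 15.3% |
| 55 (15) | 10.3% | 11.7% |
| 40 (20) | 20.7% | 22.6% |
| 40 (8) | 9.0% | 9.6% |
| 20 (18) | 38.1% | 39.0% |
| 20 (20) | 40.3% | 41.2% |

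The last two rows lie below the formula because truncation at 0 raises the mean and narrows the spread. In every case power was 78–81% for three alternatives: the interaction model with groups compared at the mean baseline, the common-slope model, and a sequential group test entered after baseline in the SAP's listed order.

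**Unequal slopes.** Baseline 55 (SD 18), 50:50 split, slopes differing by 0.3, no difference at the mean. The difference at 0 is 0.3 × 55 = 16.5 points in size. Its standard error is 20 × √(2/77.5) × √(1 + (55/18)²) = 3.21 × 3.215 = 10.3. The ratio 16.5/10.3 = 1.60 implies rejection in about 36% of trials. Simulation gave 35.7% at 0, against 4.8% for the contrast at the mean. With a true 9-point difference at the mean, simulated power at 0 was 10.5% or 66.9%, depending on the direction of the slope difference, against 79–80% at the mean.

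**The case against.** The strongest reply is that the SAP never says this test will be used. It does not say that baseline stays on the raw scale, that Type III tests are taken, or that the group main effect is the gate. The Table 3 footnote puts the p-value, adjusted means and interval under one model without the interaction. Read that way they agree and no power is lost. Listing the interaction could simply reflect the slope check described under Test of assumptions. This stands. A reader might infer that the group test is definitely made at 0, and the documents do not support that.

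A reader might also infer that most of the power is certain to go. That depends on baseline mean/SD, which the documents do not give; at a ratio of 0.5 the loss is from 80% to 71%. Nor are centring or removal of the interaction the only remedies, since a contrast at the mean baseline or a sequential test also works.

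The simulations use two groups, where the Bonferroni gate has no effect. For three or more groups with similar baselines, the same factor 1 + (m/s)² inflates the variance of each group's fitted value at 0, but power was not computed for that case.

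Finally, this could be called a mere mismatch between text and footnote. In part it is, and the footnote's model resolves it. But resolving it in favour of the body text, without a reference baseline and a named test, would leave the problem open.

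**Conclusion.** The point holds as a conditional one. The SAP gives two descriptions of the ANCOVA and does not name the test that opens the pairwise comparisons. One literal implementation, with the interaction, raw scores and the Type III group test, compares groups at a score that is the best possible on the AOS and the worst possible on the FAOS. Under that implementation, 80% power would fall to 51%, 24%, 14% and 8.5% at mean/SD of 1, 2, 3 and 5. A slope difference of 0.3 alone would give about 36% rejections at baseline 55 (SD 18). All baseline values, the residual SD and the alpha are assumptions.

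The reach is limited. These are secondary subgroup comparisons in a non-randomised study whose protocol says its sample size was not derived statistically. The Kaplan-Meier survivorship endpoint and the pre- to post-surgery tests do not use this model. The change is still worth making, because group p-values should not turn on an unstated coding choice.

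**What to change.** In Group Comparisons, state that the group p-values, adjusted means, confidence intervals and the test that opens the Bonferroni comparisons all come from the ANCOVA with group and baseline only, as the Table 3 footnote already has it. Remove the interaction from the list of components of that model.

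In Test of assumptions, make the subgroup-by-baseline term a separate F-test of equal slopes. Drop Levene's test for that purpose, since it compares variances rather than slopes.

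As a supplement, report group differences from the interaction model at the overall mean pre-operative score and at its quartiles. Do this whatever the slope test shows, so that no data-driven switch of model is introduced.

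The cost is a few sentences in the SAP and a small amount of extra analysis. No new data are needed.

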## Patient Reported Outcome Measures (PROMS)

The standard care pathway for patients undergoing Total Ankle Replacement includes the collection of Patient Reported Outcome Measures (PROMS), in some institutions. The study aims to use this data, wherever possible, to fulfill the secondary outcome measures of the study and avoid duplication of data collection. As there is some variance nationally regarding the questionnaires which are used for PROMS data collection, participants may be required to supplement one or more of the following questionnaires for the purposes of the research study:

*PROMIS*® (*Patient-Reported Outcomes Measurement Information System*) is a set of person-centered measures that evaluates and monitors physical, mental, and social health in adults and children. It can be used with the general population and with individuals living with chronic conditions.

• PROMIS Scale v1.2 - Global Health

*The Foot and Ankle Outcome Score (FAOS)* is a self-report measure that evaluates symptoms and functional limitations in individuals with generalized foot and ankle disorders. Items for the Foot and Ankle Outcome Score were adapted from the Knee Injury and Osteoarthritis Outcome Score. The FAOS is composed of the following 5 subscales: pain (9 items), other symptoms (7 items), activities of daily living (7 items), sports and recreational activities (5 items), and foot and ankle-related quality of life (4 items).

*Ankle Osteoarthritis Score (AOS)* is a reliable, validated, visual analog based, disease specific self-administered instrument designed specifically to measure disability and pain from ankle osteoarthritis. Both Pain and Disability components are used to calculate the total score. The score is from zero to one hundred with a lower score indicating more normal function. The minimally important difference for the AOS score is not known.

*Total Ankle Replacement Satisfaction*, this study will be evaluating the patient's satisfaction with their total ankle replacement post operatively (6months,1yr,2yrs,5yrs,7yrs,10yrs) utilizing a four point scale.

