# STATISTICAL CONSIDERATION

#### Sample Size

The total sample size is 200 subjects. The sample size was not calculated using statistical methods. A nonparametric statistical analysis for survivorship using the Kaplan-Meier will be applied to determine the implant survivorship.

Mechanical survivorship for total hip and knee replacement is currently thought to be approximately 10 years. This benchmark for long-term data collection is not only relevant to the safety and survivorship of the implant but, also to provide assurances that for the introduction of new implants, a data collection plan is in place for ongoing evaluations and reporting.

The information gained from this data collection will be analyzed at times based on potential publication periods around 2, 5, and 7 years with a final analysis after all subjects haven completed all follow-up requirements at the 10 year final visit. In addition, at time points determined by the investigators and/or Wright Medical will be evaluated as needed or required for additional analysis of data for reporting and/or publication purposes will be done throughout the study.

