### **STUDY DESIGN**

#### **Overview**

This study is a prospective, multi-site, multi-year post-market, follow-up clinical trial to evaluate the long-term survivorship of the INFINITY® Total Ankle System in the treatment of ankle joint damaged caused by severe rheumatoid, post- traumatic, or degenerative arthritis, as well as for patients with a failed previous ankle surgery. Prior to surgery, medical history, demographic, radiographic parameters and disease severity by COFAS type, varus/valgus deformity and function and quality of life of patients were collected.

At Day 0 (Surgery Day), information related to the subject's operation will be collected and recorded according to the Operative Information Case Report Forms, which included the following: Primary diagnosis, any previous surgery to index joint, date of operation, site location, surgical approach, instrumentation type (standard) or (additional approved INFINITY® instrumentation), concomitant operative procedures, cement use, intraoperative complications, and product description and eight-digit product code for all components implanted. Subjects were to return for clinical, functional and radiographic evaluations and safety evaluations at 6 months, 1 year, 2 years, 5 years, 7 years and 10 years post-surgery. The study planned to enroll 200 or more subjects in the US with 10 investigational sites, however, 155 patients participated when enrollment was closed. The study subjects included are those with ankle joints damaged by severe rheumatoid arthritis, post-traumatic disease, and degenerative arthritis and implanted with the INFINITY® Total Ankle System.

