### STATISTICAL METHODS

### **General Considerations**

All enrolled subjects who underwent total ankle replacement implanted with INFINITY™ or INBONE® product configurations listed in Table 1 will be included in the analysis. All data will be summarized for all subjects at baseline and at every post-surgery visit, namely at 6 months, 1, 2, 5, 7, and 10 year post surgery.

Categorical data will be displayed as frequency and percent, and continuous data will be displayed using descriptive statistics (N, mean, standard deviation, quartiles, minimum and maximum, CI). Subgroup analyses will be conducted for all the patient reported outcomes: PROMIS Global Health AOS and FAOS. Subgroup analysis and comparisons will be presented for the following factors:

- surgical instrumentation type (standard vs additional approved instrumentation),
- type of primary disease diagnosis (Rheumatoid arthritis, Post traumatic, Degenerative);
- COFAS type (Types 1-4);
- Varus and/or valgus degree of deformity
- Radiographic radiolucency.

Radiolucency factors will be categorized independently with respect to linear and cystic radiolucency as follows:

Linear radiolucency:	Group 1: Present Linear radiolucency (>2mm)
	Group 2: Absent Linear radiolucency (>2mm)
Cystic radiolucency:	Group 1: Present Cystic radiolucency (>5mm)
	Group 2: Absent Cystic radiolucency (>5mm)

Subgroup analysis of the patient satisfaction of their total ankle replacement post operatively will only be done for surgical instrumentation type.

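### Pairwise subgroup comparisons use single-step Bonferroni after the overall test; Holm's step-down gives the same family-wise protection with slightly more power.

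*SAP*

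**What the plan says.** The SAP compares subgroups on PROMIS, AOS and FAOS at each post-surgery visit by ANCOVA. Under Group Comparisons, "Bonferroni pairwise adjusted comparison of means will be done when significant differences among the group is established". The sentence is written once for all factors. General Considerations lists among them "type of primary disease diagnosis (Rheumatoid arthritis, Post traumatic, Degenerative"), which has three levels, and "COFAS type (Types 1-4"), which has four.

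No significance level is stated. The nearest indication is "Adjusted mean of subgroups with 95% confidence intervals will be presented".

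The model behind the overall test is described in two ways. The text says "The components of the ANCOVA model are: baseline scores, subgroups or independent factor and subgroup-by-baseline interaction". The footnote to Table 3 in the same section describes group plus baseline only. The section on testing assumptions plans a check of slope equality but does not say what follows if it fails.

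**The concern.** The rule first requires a significant overall test and then divides alpha by the full number of pairs, as though no test had come before. With three groups, any two equal pairs force all three to be equal. Once equality of all three has been rejected, at most one pair can still be truly equal, and dividing by three is more than the error rate requires. Even without that argument, single-step Bonferroni is never more powerful than Holm's step-down, which has the same guarantee.

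What is at stake is power in already thin comparisons. "155 patients participated when enrollment was closed", against a planned 200; the SAP (Missing Data) excludes patients who lack the data an analysis needs; and follow-up runs ten years. Real differences between diagnosis groups or COFAS types could be missed without any gain in protection.

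**Working it through.** **Inputs.** From the documents: 155 patients, three diagnosis groups, four COFAS types. The plan offers no power or error figure to reproduce; the protocol says of its target that "The sample size was not calculated using statistical methods", and of one scale that "The minimally important difference for the AOS score is not known". Assumed: two-sided 5%, residual SD 1, and the group sizes and effects shown below.

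**Thresholds.** Three groups give 3 pairs, so Bonferroni tests each at 0.05/3 = 0.0167 (critical t 2.42 at 150 df, against 1.98 at 0.05). Four types give 6 pairs, so 0.05/6 = 0.0083. Holm orders the p-values and uses 0.05/3, 0.05/2, 0.05 in turn (for six pairs: 0.05/6, 0.05/5, down to 0.05). Its first step equals Bonferroni and later steps are looser, so it rejects everything that Bonferroni rejects.

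**How many pairs can still be equal after a valid overall rejection.** Three groups: at most 1 of 3. Four groups: splitting them 3+1 leaves 3 equal pairs, 2+2 leaves 2, and 2+1+1 leaves 1, so at most 3 of 6. Shaffer's procedure uses these counts: each pair at 5% for three groups, starting at 5%/3 for four.

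**Family-wise error, simulated, with the overall test on the same adjusted means.**
- SAP rule, three groups: 3.8–4.2% when all are equal, and about 1.7% when one differs. The latter is what one remaining true null tested at 0.05/3 should give. Over the three- and four-group settings with one group different, the rule uses 1.6–2.3% of its 5%.
- Overall test then unadjusted pairs, three groups: 4.9–5.1%.
- Overall test then unadjusted pairs, four groups: about 12% with one group different, about 10% with two pairs of equal groups.
- Overall test then Shaffer, three and four groups: 3.4–5.0%.

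**Per-pair power, overall test then Bonferroni or Shaffer.**

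| Assumed groups and difference | Bonferroni | Shaffer |
|---|---|---|
| 52/52/51, one group 0.5 SD away | 55% | 65% |
| 52/52/51, one group 0.6 SD away | 73% | 82% |
| 20/65/70, small group 0.6 SD away | 47% | 55% |
| 20/65/70, group of 65 0.5 SD away | 32%; 69% | 48%; 75% |
| 10/57/38 (attrition), group of 57 0.5 SD away | 17%; 48% | 28%; 56% |
| Four groups of about 39, one 0.6 SD away | 49% | 57% |

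In runs of this kind Holm gained roughly 1 to 5 points over Bonferroni. Over a wider three-group grid (effects 0.2–1.2 SD, equal to very unequal sizes), unadjusted pairs after the overall test, which is Shaffer's rule for three groups, gained 0 to about 18 points per pair: 57% of pair scenarios below 7, 31% between 7 and 15, 12% above 15. The median gain was 10 points where the unadjusted-pair power was 20–50%, 14.5 at 50–70%, 10 at 70–90% and 1 above 90%.

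**Where the loss arises.** The overall test itself costs Bonferroni at most 0.6 points. The divisor does the rest. Hand check without the overall test, 52 per group: a difference with 80% power at 0.05 has a standardised mean of 1.960 + 0.842 = 2.802. At 0.05/3 the critical z is 2.394, and Φ(2.802 − 2.394) = Φ(0.408) = 66%, a loss of 14 points.

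**The interaction model.** With an interaction and an uncentred baseline, the group term tests equality at a baseline score of 0, while the pairs compare means at the average baseline. Assume 52/52/51, mean baseline 60, baseline and residual SD 20, slopes 0/0.4/0.8, and adjusted means equal at baseline 60 (4,000 runs). The overall test is significant about 92% of the time. Unadjusted pairs then have a family-wise error of about 12%, the SAP rule about 4%. With slopes 0.2/0.4/0.6 unadjusted pairs give 5.7%. When the overall test is taken at the mean baseline, unadjusted pairs give 4.9–5.7% over the slope sets tried, with simulation error of about √(0.05 × 0.95/4,000) = 0.3 points.

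**The case against.** The best defence is that Bonferroni is robust. It holds 5% whatever the overall test examines, which matters because the SAP has not settled its ANCOVA model. A rule that leans on the overall test can reach about 12% under the model written in the text. This stands against Shaffer's procedure as things are now. It does not touch Holm, which needs no preliminary test.

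A reader might infer that the SAP pays for the same error twice and that Bonferroni can simply be dropped once the overall test is significant. The documents do not support that. The overall test costs under one point, and the same sentence governs the four COFAS types, where unadjusted pairs would reach about 12%.

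A reader might also take 7 to 15 points as the loss in this trial. No effect, SD or group size in the documents yields such a figure; the range describes moderate-power cases under assumed inputs.

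Two further points stand in part. The listed Tables 2.2.5, 2.3.5 and 2.4.5 plan a two-group contrast of rheumatoid arthritis against the other diagnoses, which needs no pairwise adjustment. If rheumatoid arthritis were the group of 20 and lay 0.6 SD away, its power would be Φ(0.6/√(1/20 + 1/135) − 1.96) = Φ(0.54), about 70%. That covers neither degenerative against post-traumatic disease nor the COFAS types. Second, Bonferroni has matching simultaneous intervals and step-down tests do not. The SAP asks for 95% intervals but does not call for simultaneous ones.

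**Conclusion.** The stated rule is valid and is not an error. It is needlessly conservative within one outcome, visit and factor. Holm improves on it under any of the models described, by roughly 1 to 5 points of per-pair power at the effects and sizes tried. Shaffer's larger gain depends on a condition that the SAP does not yet meet. That Holm is at least as powerful as Bonferroni does not depend on the assumptions; the size of every gain does, including the assumed two-sided 5% level. Severity is low: these are secondary subgroup comparisons with no power target, and the larger multiplicity across scores, visits and factors is a separate matter.

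**What to change.** Replace the Bonferroni sentence with one along these lines: for every factor with three or more levels, pairwise adjusted means will be compared by Holm's step-down procedure at a two-sided family-wise 5% within each outcome and visit. The overall test may stay in front of it. Because this wording needs no count of levels, it also covers the varus/valgus factor, for which the SAP gives none.

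Shaffer's step-down (each pair at 5% for the three diagnoses, starting at 5%/3 for COFAS type) should be used only if the SAP also states that the overall test is of the same adjusted means as the pairs. That means either group plus baseline without interaction, as in the Table 3 footnote, or a group test at the mean baseline. The text and the footnote should be reconciled in any case.

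The cost is one sentence and a step-down adjustment of the pairwise p-values. The drawback is the lack of matching simultaneous intervals, so the 95% intervals in Table 3 should be labelled as unadjusted.
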